### **3.5 Rationale for timing of observations**

The maximum concentration is anticipated to be at the end of the infusion. The concentration will decrease sharply and will be nearly undetectable at 24 hours. The observations are focused at the time immediately after the end of infusion and extend out to 24 hours. Baseline PD ECG data will be collected in the hour prior to infusion at three separate timepoints. Triplicate ECG analysis will reduce the variability of the interval determinations. Concentration data will be obtained at baseline, at the mid-point of infusion, and immediately after each ECG timepoint.

### **3.6 Choice of healthy male volunteers**

MCI-186 was well-tolerated at the doses chosen in healthy volunteers. Healthy volunteers will facilitate the collection of ECG data with less variability.

It is unlikely that unusual susceptibility to repolarization prolongation would be found in healthy females with clearly normal QTc values during screening and at baseline. Selection of only male volunteers is further justified as the effects of MCI-186 will be determined based on subject-specific baseline values.

### **3.7 Choice of QT correction**

As no HR effects are anticipated, Fridericia correction will provide adequate adjustment for HR effects on the QT interval.

### **3.8 Cardiology Core Laboratory**

A cardiology core laboratory highly experienced in such studies will provide centralized and standardized interpretation of PD ECGs. Advance systems will extract technically optimal ECGs from the continuous Holter data. ECG interpretation will be by manual adjudication

of semi-automated interval determination in a digital environment. A small number of expert MD electrocardiographers will be assigned, and a single reader will review all studies from any individual subject under blinded condition.

## **4 SELECTION AND WITHDRAWAL OF SUBJECTS**

The Sponsor does not operate a Protocol waiver system for eligibility criteria.

### **4.1 Number of subjects**

It is planned to randomize 27 subjects in this study.

### **4.2 Recruitment methods**

Subjects will be recruited from a database of volunteers or *via* media advertisements, if appropriate. Subjects will be recruited according to study center's Standard Operating Procedures. All recruitment material will be approved by the Institutional Review Board (IRB) prior to implementation.

A sufficient number of subjects will be screened to ensure the planned sample size will be achieved. Each subject will be screened according to the criteria described in Sections 4.3 and 4.4. Only subjects who are eligible for the study will be randomized.

### **4.3 Inclusion criteria**

A subject will be eligible for enrolment in the study if ALL of the following criteria apply:

1. Healthy males aged 20 to 55 years (both inclusive) at signature of the Informed Consent Form (ICF).
2. Able to provide written informed consent to participate in this study after reading the ICF, and after having the opportunity to discuss the study with the Investigator or designee, before any screening or study related procedures take place.
3. In the Investigator's opinion, subject is able to understand the nature of the study and any risks involved in participation, and willing to cooperate and comply with the protocol restrictions and requirements.
4. A body weight of  $\geq 45$  kg and a body mass index (BMI) ranging from 18 to 30  $\text{kg}/\text{m}^2$  (both inclusive) at screening and Day -1.
5. Good health and free from clinically significant illness or disease in the opinion of the investigator on the basis of a physical examination, medical history, ECG, vital sign, and clinical laboratory test (biochemistry, hematology, coagulation and urinalysis) at screening and Day -1.
6. Male subjects must practice effective contraception during the study, from the time of the first dose of IMP until 14 days after the last dose of IMP.

### **4.4 Exclusion criteria**

A subject will NOT be eligible for this study if ANY of the following criteria apply:

1. Subjects with  $\text{PR} > 240$  msec,  $\text{QRS} \geq 120$  msec, or  $\text{QTcF} > 450$  msec on the screening or Day -1 ECG, or any clinically significant electrocardiographic abnormality in the opinion of the Investigator.
2. Subject who has a history of cardiac disease or arrhythmias that can cause QTc prolongation.
3. Subject who has a family history of Torsade de Pointes, long-QT syndrome, hypokalemia or sudden death.
4. Subjects with potassium levels outside of the laboratory reference ranges at screening or Day -1.

5. Subjects with clinically significant deviations from normal in physical examination, vital signs, ECG or clinical laboratory test at screening or Day -1 in the opinion of the Investigator.
6. Presence or history of any clinically significant disease or organ dysfunction in the opinion of the Investigator.
7. Presence or history of allergy to food, any medical product or relevant excipient that is of clinical significant.
8. Subjects were previously administered MCI-186.
9. Presence or history of alcohol abuse or a positive alcohol test.
10. Presence or history of drug abuse or a positive drug screen test.
11. Positive test for hepatitis C virus antibody, hepatitis B surface antigen, human immunodeficiency virus (HIV) antigen/antibody or syphilis test at screening.
12. Participation in another trial within 12 weeks or 5 times the half-life of the drug whichever is longer before providing a signed ICF. For biologics, the minimum period is at least 24 weeks or the period of the pharmacodynamic effect, or 10 times the half-life of the drug, whichever is longer before providing a signed ICF.
13. Donate blood more than 200 mL within 4 weeks, 400 mL within 12 weeks or 1000 mL within 52 weeks, respectively before providing a signed ICF.
14. Donate plasma or platelet component within 2 weeks before providing a signed ICF.
15. Use of any prescription or non-prescription medications including herbal remedies and vitamin/mineral/protein supplements, except for acetylsalicylic acid, within 7 days prior to IMPs dosing.
16. Use of tobacco or nicotine containing products for 24 hours before each visit of screening or Day -1.
17. Consumption of alcohol, xanthines, or grapefruit containing products for 24 hours before each visit of screening or Day -1.

#### **4.5 Withdrawal of individual subjects**

A subject will be withdrawn if ANY of the following criteria are met:

- The subject wishes to withdraw from further participation.
- The subject is significantly noncompliant with the Protocol.
- Continuing in the study would be detrimental to the subject's safety in the opinion of the Investigator, e.g.,
  - The subject experiences intolerable AEs or serious AEs (SAEs).
  - The subject has clinically significant changes in safety parameters at any of the post-dose time points, as confirmed with a repeat assessment performed as soon as possible after the initial out-of-range result.
  - The subject has an increase in QTcF to  $\geq 500$  msec or increase of  $\geq 60$  msec from baseline (pre-dose on Day 1), as confirmed with three consecutive ECGs taken at least five minutes apart in a 30-minute period.

In addition, a subject may be withdrawn at any time for reason(s) other than those listed here.

If a subject is discontinued prematurely from the study, the date the subject is withdrawn from the study and the reason for withdrawal will be recorded on the electronic case report form (eCRF).

In case of withdrawal of a subject, the Follow-up Visit assessments should be performed, as far as possible (Section 5.1.3).

Any withdrawal due to an AE or for any safety reason should be assessed for seriousness according to Section 8.2.

Any unresolved AE or SAE will be followed up according to Section 8.9.

In the event that a subject elects not to return to the study center for the Follow-up Visit, the Investigator must make every effort to contact the subject to review all AEs. In the event that a subject drops out of the study at any time, the reason for discontinuation must be fully documented in the source documents and the eCRF. The study center personnel will document the AEs and any other assessments in the source documents and will make every effort to complete all required Follow-up Visit assessments.

Subjects who are withdrawn from the study following Randomization may not re-enter the study.

Subjects withdrawn for non-treatment-related reasons may be replaced at the discretion of the Sponsor and Investigator. Replacement subjects will receive the treatments intended for the withdrawn subject.

#### **4.6 Lifestyle restrictions**

Subjects will be advised that they must adhere to the following restrictions by investigator and staff in the study center:

##### **4.6.1 Attendance**

- Subjects must be available to attend visits according to the Protocol.
- Subjects must be available for overnight stays in the study center for 2 nights in each 3 period.

##### **4.6.2 Alcohol restrictions**

- Subjects should refrain from consuming food or drink containing alcohol in the 24 hours before each visit and whilst confined to the study center.
- Subjects should avoid excessive consumption (>16 g as pure alcohol per day) of food or drink containing alcohol at all other times from the Screening visit until the Follow-up assessment.

##### **4.6.3 Xanthines**

- Subjects should refrain from consuming food or drink containing caffeine and methylxanthine, including coffee, tea, cola, energy drinks or chocolates in the 24 hours before each visit and whilst confined to the study center.
- Subjects should avoid excessive consumption (more than five cups of coffee or equivalent per day) of food or drink containing caffeine and methylxanthine (e.g., coffee, tea, cola, energy drinks or chocolates) at all other times from the Screening visit until the Follow-up assessment.

##### **4.6.4 Other food restrictions**

Subjects should refrain from consuming food or drink containing grapefruit (including marmalade and fruit juices) in the 24 hours before each visit and whilst confined to the study center.

#### **4.6.5 Smoking**

No smoking or using tobacco- or nicotine-containing products (snuff, chewing tobacco, cigarettes, cigars, pipes, e-cigarettes or nicotine replacement products) in the 24 hours before each visit and whilst confined to the study center.

#### **4.6.6 Contraception**

- Subjects (males) with partners of child-bearing potential must use a barrier method of contraception (i.e., male condom with spermicide) in addition to a second method of acceptable contraception used by their female partners. The additional contraception methods include:
  - Placement of an intrauterine device
  - Established use of oral hormonal methods of contraception associated with inhibition of ovulation
  - Male sterilisation (with the appropriate post-vasectomy documentation of the absence of sperm in the ejaculate).
  - Bilateral tubal ligation
  - Diaphragm with spermicide
- Subjects in a same sex relationship must use condom during sexual intercourse from the time of the first dose of IMP until 14 days after the last dose of IMP.
- Subjects must not donate sperm for the duration of the study, from the time of the first dose of IMP until 14 days after the last dose of IMP.
- Subjects must not have unprotected sexual intercourse during the study.

#### **4.6.7 Diet**

- While confined to the study center, subjects will receive standardised meals at scheduled times.
- Subjects will be required to fast (except for water) for at least 4 hours prior to routine safety blood sampling.
- No food or drink containing grapefruit (including marmalade and fruit juices) will be allowed in the 24 hours before each visit and whilst confined to the study center.
- Subjects should refrain from ingesting food or drink containing poppy seeds in the 72 hours before the Screening visit and Day -1 to avoid the occurrence of false positive opioid drug screen results.

#### **4.6.8 Physical activity restrictions**

- Must not participate in heavy physical training or excessive exercise (e.g., long distance running, weight lifting or any physical activity to which the subject is not accustomed) from seven days before first dose of IMP, during the study and until the Follow-up assessment.

#### **4.6.9 Blood donation**

- Donate blood more than 200 mL within 4 weeks, 400 mL within 12 weeks or 1000 mL within 52 weeks, respectively before providing a signed ICF.

- Donate plasma or platelet component within 2 weeks before providing a signed ICF.
- Subjects must agree not to donate blood for 3 months after the Follow-up assessment.

## **5 STUDY PLAN**

Study assessments are summarized in the time and events schedule in Table 1

**Table 1 Time and events schedule**

Study Period	Screen-ing	Confinement (Next IMP dosing must keep at least 72 hr and up to 9 days washout after starting the previous dosing)													Follow-up 2 (only Period 3)					
		-28 to -3	-1	1	Pre-dose	0	0.5 h	1 h	75 min	90 min	105 min	2 h	3 h	4h	6h	8h	12h	24h		
Study Day	-28 to -3		-1	1															2 5-9	
Time point in Relation to Start of Infusion																			(only Period 3)	
Informed consent	X																			
Confinement a			←														→			
Outpatient	X																		X	
Demography & medical history	X																			
Inclusion/exclusion criteria	X	X	X																	
Randomization			X																	
Physical examination	X	X b	X b				X b											X b	X	
Weight	X	X																X	X	
Height	X																			
BMI	X	X																		
Vital signs c	X	X	X				X												X	X
Routine safety 12-lead ECG d	X e	X	X				X											X	X	
Continuous 12-lead Holter (PD ECGs extracted in triplicate) f			X g		X	X	X	X	X	X	X	X	X	X	X	X	X	X		
Drugs of abuse & alcohol test	X	X																		
Hematology, biochemistry, coagulation & urinalysis	X	X																	X	X
Serology	X																			
IMP administration (infusion)			←	→																
PK sampling (blood) h		X		X	X	X	X	X	X	X	X	X	X	X	X	X	X	X		
Adverse events	←																→			
Concomitant medications	←																→			

a: Subjects will be admitted 3 times to the study center (on Day -1 in each period) and discharged in the morning of Day 2 in each period.

b: Abbreviated physical exam

c: Blood pressure, pulse rate and body temperature

- d: Using conventional bedside equipment
- e: Routine safety ECG in triplicate at Screening only
- f: Mandatory rest from 10 minutes prior to until 5 minutes after each timepoint
- g: Predose at -45, -30 and -15 minutes
- h: No sooner than 5 minutes after associated PD ECG timepoint

## **5.1 Subject informed consent**

Prior to performing any study procedures, the Investigator (or designated personnel) will ensure that the subject is given full and adequate oral and written information about the study and the subject must sign the ICF, as described in Section 11.2.1.

### **5.1.1 Screening**

Screening assessments will be performed from Day -28 to Day -3.

At Screening, subjects will be requested to attend the study center after a 4-hour fasting period (apart from water). Written informed consent will be obtained before any screening procedures are performed. The following assessments will be performed (refer to Table 1 for further details):

- Written informed consent.
- Demography and medical history.
- Verify inclusion/exclusion criteria.
- Physical examination (including height, weight and BMI).
- Vital signs (including supine blood pressure, pulse rate and body temperature).
- Routine safety 12-lead ECG in triplicate.
- Screening for drugs of abuse and alcohol.
- Routine laboratory evaluations (hematology; biochemistry; coagulation; urinalysis).
- Serology.
- AE and prior and concomitant medication recording.

### **5.1.2 Confinement period**

Subjects who successfully complete Screening will return to the study center on Day -1 will remain on-site until Day 2 in each 3 period. Inclusion and exclusion criteria will be reviewed to confirm eligibility on admission. No IMP will be administered on Day -1.

The following assessments will be performed (refer to Table 1 for further details and time points):

#### **Day -1**

- Verify inclusion/exclusion criteria.
- Abbreviated physical examination (including weight and BMI)
- Screening for drugs of abuse and alcohol.
- Vital signs (blood pressure, pulse rate and body temperature).
- Routine safety 12-lead ECG.
- Routine laboratory evaluations (hematology; biochemistry; coagulation; urinalysis).
- AE and concomitant medication recording.

#### **Day 1 (pre-dose)**

- Verify inclusion/exclusion criteria.
- Abbreviated physical examination

- Vital signs (blood pressure, pulse rate and body temperature)
- Routine safety 12-lead ECG.
- Eligible subjects will proceed to randomisation and dosing on Day 1 and remain in the study center until completion of assessments on Day 2.
- Rest period for 10 minutes prior to and for 5 minutes after each of the PD ECG timepoints at 45, 30 and 15 minutes before start of infusion.
- PK blood sampling for MCI-186.

**Day 1 (post-dose)**

- IMP administered over 1 hour
- Abbreviated physical examination
- Vital signs (blood pressure, pulse rate and body temperature) at 1 hour post-start of infusion.
- Routine safety 12-lead ECG at 1 hour post-start of infusion.
- Rest period for 10 minutes prior to and for 5 minutes after each of the PD ECG timepoints at 30, 60, 75, 90 and 105 minutes, and at 2, 3, 4, 6, 8 and 12 hours post-start of infusion.
- During each rest period, study personnel will check the integrity of Holter monitoring electrodes and functioning of the recorder.
- PK blood sampling for MCI-186 no sooner than 5 minutes but no later than 7 minutes after the timepoints in relation to start of infusion at 30, 60, 75, 90, and 105 min; and no sooner than 5 minutes but no later than 10 minutes after the timepoints in relation to start of infusion at 2, 3, 4, 6, 8 and 12 hours.
- AE and concomitant medication recording.

**Day 2 (24 hours post-dose)**

- Abbreviated physical examination (including weight).
- Vital signs (blood pressure, pulse rate and body temperature).
- Routine safety 12-lead ECG.
- Rest period for 10 minutes prior to and for 5 minutes after the PD ECG timepoint at 24 hours post-start of infusion.
- During the rest period, study personnel will check the integrity of Holter monitoring electrodes and functioning of the recorder.
- Discontinue Holter monitor no sooner than 5 minutes after the PD ECG timepoint at 24 hours post-start of infusion.
- Routine laboratory evaluations (hematology; biochemistry; coagulation; urinalysis).
- PK blood sampling for MCI-186 no sooner than 5 minutes and no later than 10 minutes after the ECG timepoint at 24 hours post-start of infusion.
- AE and concomitant medication recording.

### **5.1.3 Follow-up**

Subjects will return to the study center between Day 5 -9 inclusive of Period 3 for a Follow-up Visit. The following assessments will be performed (refer to Table 1 for further details):

- Physical examination (including weight).
- Vital signs (blood pressure, pulse rate and body temperature).
- Routine safety 12-Lead ECG.
- Routine laboratory evaluations (hematology; biochemistry; coagulation; urinalysis).
- AE and concomitant medication recording.

### **5.1.4 Unscheduled visits**

An unscheduled visit is defined as any visit to the study center outside of the Protocol-specified time points due to safety reasons or when a repeated measurement is required (e.g., obvious measurement errors, measuring device failure, confirmation of out-of-range results), where the subject is seen by study personnel.

Additional unscheduled samples for safety assessments may be performed at the discretion of the Investigator, if deemed necessary. All unscheduled visits and assessments performed during the visits will be recorded in the eCRF.

## **6 STUDY PROCEDURES**

Procedures will be performed according to the time and events schedule (Table 1). A priority order will be in effect when more than one assessment is required at a particular time point, as follows: ECG extraction window (from nominal time to 5 minutes after nominal time), PK sample, vital signs, safety ECG. Time windows for relevant assessments will be described in a separate document.

### **6.1 Demography**

Date of birth, sex, weight, height and race will be recorded in the eCRF.

### **6.2 Medical history**

Any significant and relevant past conditions and any current medical conditions prior to Screening will be recorded in the eCRF.

### **6.3 Medication**

At Screening, subjects will be asked what medications they have taken during the last 30 days. Only medication taken in the two weeks prior to administration of IMP will be recorded in the eCRF as prior medication.

Concomitant medication is defined as any medication, other than the IMP, which is taken from the start of IMP infusion to the Follow-up assessment, including prescription, herbal and over-the-counter medications. All concomitant medications taken while the subject is participating in the study will be recorded in the eCRF with their daily dosage, route, duration, and reasons for administration.

#### **6.3.1 Permitted medication**

Medicines which, in the opinion of the Sponsor and Investigator, will not interfere with the study procedures or compromise safety may be used, e.g., acetylsalicylic acid (aspirin) for mild analgesia. However, any other concomitant medication may be given only if deemed strictly necessary for the subject's welfare by the Investigator.

#### **6.3.2 Prohibited medication**

Subjects must not participate in any other clinical study involving administration of an IMP for the duration of the current study.

Subjects must not take any prescribed or non-prescribed systemic or topical medication (including herbal remedies) unless, in the opinion of the Investigator and Sponsor, the medication will not interfere with the study procedures or compromise safety.

#### **6.3.3 Rescue medication**

There is no known antidote for MCI-186. Full resuscitation facilities will be available at all times.

### **6.4 Continuous 12-lead Holter electrocardiogram and Pharmacodynamic ECGs**

Continuous 12-lead Holter data will be obtained from all subjects beginning at least 1 hour prior to and continuing at least until 24 hours after the start of infusion. Triplicate 10 second 12-lead PD ECGs will be extracted from the 5-minute period starting at the following timepoints in relation to start of infusion: -45, -30 and -15 min; and 30, 60, 75, 90, and 105 min, and 2, 3, 4, 6, 8, 12 and 24 hours.

Prior to each of these timepoints, subjects should observe at least 10 minutes of rest and rest will continue for 5 minutes after each timepoint. During each rest period, study personnel will check the integrity of Holter monitoring electrodes and functioning of the recorder. A detailed procedure will be described in a separate document.

Triplicate 12-lead PD ECGs of 10-second duration will be extracted from the Holter data by the cardiology core laboratory during the 5-minute period starting at each of the time points. PK collection must be performed no sooner than 5 minutes after each of these times.

## **6.5 Pharmacokinetic assessments**

Blood samples for MCI-186 will be collected pre-dose and no sooner than 5 minutes but no later than 7 minutes after the timepoints in relation to start of infusion at 30, 60, 75, 90, and 105 min; and no sooner than 5 minutes but no later than 10 minutes after the timepoints in relation to start of infusion at 2, 3, 4, 6, 8, 12 and 24 hours.

The analysis will be performed only on samples from subjects receiving active drug.

Blood samples will be packed in dry ice and sent by courier to:

[REDACTED]

Primary samples will be sent by courier from study center to [REDACTED]

[REDACTED] Contingency samples will be shipped after primary samples arrive.

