#### **2.1.4 Secondary endpoints**

- Assessment of HR, PR interval, QRS interval, and QTcF by timepoint
- Categorical outliers for QTcF interval (absolute value and change from baseline) and other 12-lead ECG parameters
- Incidence of abnormalities in ECG morphology
- PK parameters of MCI-186
- Incidence of adverse events (AEs) and serious adverse events (SAEs), vital signs, safety 12-lead ECG variables, laboratory tests and physical examination

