### 10.4 Statistical analysis

#### 10.4.1 General considerations

All individual subject data will be listed.

The statistical analysis will be performed using SAS® Version 9.2 or higher.

All variables will be summarized by treatment.

Unless otherwise stated, continuous data will be summarized descriptively including: number of subjects (N), number of observations (n), mean, standard deviation (SD), minimum, median and maximum. Categorical data will be summarized using frequency tables (frequency and percent).

The PK concentrations will be summarized by planned sampling time.

A detailed SAP will be prepared and approved prior to the study database lock which will include all detailed data handling and statistical methods. Any deviations from the planned analyses will be described and justified in the final integrated Clinical Study Report.

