**Table 1 Time and events schedule**

Study Period	Screen-ing	Confinement (Next IMP dosing must keep at least 72 hr and up to 9 days washout after starting the previous dosing)													Follow-up 5-9 (only Period 3)			
		-28 to -3	-1	1	Pre-dose	0	0.5 h	1 h	75 min	90 min	105 min	2 h	3 h	4h	6h	8h	12h	24h
Study Day	-28 to -3																	2
Time point in Relation to Start of Infusion																		
Informed consent	X																	
Confinement a			←-----→															
Outpatient	X																	X
Demography & medical history	X																	
Inclusion/exclusion criteria	X	X	X															
Randomization				X														
Physical examination	X	X b	X b				X b											X b X
Weight	X	X																X X
Height	X																	
BMI	X	X																
Vital signs c	X	X	X				X											X X
Routine safety 12-lead ECG d	X e	X	X				X											X X
Continuous 12-lead Holter (PD ECGs extracted in triplicate) f			X g		X	X	X	X	X	X	X	X	X	X	X	X	X X	
Drugs of abuse & alcohol test	X	X																
Hematology, biochemistry, coagulation & urinalysis	X	X																X X
Serology	X																	
IMP administration (infusion)				←-----→														
PK sampling (blood) h			X	X	X	X	X	X	X	X	X	X	X	X	X	X		
Adverse events			←-----→															
Concomitant medications			←-----→															

a: Subjects will be admitted 3 times to the study center (on Day -1 in each period) and discharged in the morning of Day 2 in each period.

b: Abbreviated physical exam

c: Blood pressure, pulse rate and body temperature

d: Using conventional bedside equipment

e: Routine safety ECG in triplicate at Screening only

f: Mandatory rest from 10 minutes prior to until 5 minutes after each timepoint

g: Predose at -45, -30 and -15 minutes

h: No sooner than 5 minutes after associated PD ECG timepoint

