##### 5.2 Analysis Time Window for Visits

- 1) Analysis time windows for blood sampling for PK measurements are as follows.

Pre-dose	Before dosing
0.5 h after dosing	Scheduled time + 5 to 7 minutes
1 h after dosing	Following completion of dosing + 5 to 7 minutes
75 min, 90 min and 105 min after dosing	Scheduled time + 5 to 7 minutes
2 h, 3 h, 4 h, 6 h, 8 h, 12 h and 24 h after dosing	Scheduled time + 5 to 10 minutes

2) Analysis time windows for vital signs and safety 12-lead ECG are as follows.

Screening (Day -28 to Day -3)	Not specified
Hospitalization (Day -1)	Not specified
Before dosing (Day 1)	From the time of waking up until the time when Holter ECG rest was secured (45 minutes before starting administration)
1 h after dosing (Day 1)	Scheduled time ± 20 minutes
24 h after dosing (Day 2)	From wake-up to scheduled time + 1 hour (25 hours after start of administration)
Follow-up (Day 7 ± 2 days)*	Not specified

\*: Period 3 only

3) Analysis time windows for physical examinations are as follows.

Screening (Day -28 to Day -3)	Not specified
Hospitalization (Day -1)	Not specified
Before dosing (Day 1)	From the time of waking up until the time when Holter ECG rest was secured (45 minutes before starting administration)
1 h after dosing (Day 1)	Scheduled time + 1 hour 30 minutes
24 h after dosing (Day 2)	From wake-up to scheduled time + 1 hour (25 hours after start of administration)
Follow-up (Day 7 ± 2 days)*	Not specified

\*: Period 3 only

4) Analysis time windows for blood and urine sampling at the safety laboratory tests are as follows.

Screening (Day -28 to Day -3)	Not specified
Hospitalization (Day -1)	Not specified
24 h after dosing (Day 2)	Blood sampling: From getting up to before breakfast Urine collection: From getting up to before breakfast
Follow-up (Day 7 ± 2 days)*	Not specified

\*: Period 3 only

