## 7.8 Pharmacokinetic Assessments

### 7.8.1 Analysis of Individual Plasma Concentrations

All measured plasma concentrations will be listed.

Plasma concentrations will be summarized at each scheduled sampling time point by each MCI-186 group (60 mg group and 300 mg group). The following descriptive statistics will be calculated: N (number of subjects), n (number of valid observations), arithmetic mean, SD, CV%, minimum, median, maximum, geometric mean and geometric CV%. Nominal sampling times will be displayed in the summary. For the calculation of the descriptive statistics other than geometric mean and geometric CV%, concentration values reported as BLQ will be set to 0. For the calculation of the geometric mean and geometric CV%, concentration values reported as BLQ will be set to  $\frac{1}{2}$  of LLOQ.

CV% and Geometric CV% will be calculated as follows:

$$CV\% = \frac{SD}{\text{arithmetic mean}} \times 100$$

$$\text{Geometric CV\%} = [\exp(\sigma^2) - 1]^{1/2} \times 100$$

where  $\sigma$  represents the SD computed on the natural logarithmic transformed concentrations.

To visualize the concentration-time profiles of each MCI-186 group, the following plots will be produced in linear and semi-logarithmic scales:

1. Individual subject observed and predicted concentration-time plot with each MCI-186 group (60 mg group and 300 mg group) overlaid in one graph by subject.
2. Individual subject observed concentration-time plot overlaid in one graph by each MCI-186 group (60 mg group and 300 mg group).
3. Mean observed and predicted concentration-time plot with each MCI-186 group (60 mg group and 300 mg group) overlaid in one graph.
4. Mean observed concentration-time plot with each MCI-186 group (60 mg group and 300 mg group) overlaid in one graph.

In the summary tables, arithmetic mean, SD, minimum, median, maximum and geometric mean will be presented with the number of significant digits which individual concentrations are reported. In addition, CV%, and geometric CV% will be presented with 1 decimal place.

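### Do two timings for the 1 h PK sample, and the lack of a sample at the end of infusion, call for a change to the plan?

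*Protocol*

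**What the plan says.** - **Protocol window.** Protocol 5.1.2 (Day 1, post-dose) and 6.5 count the 1 h sample from the start of infusion, "no sooner than 5 minutes but no later than 7 minutes after the timepoints in relation to start of infusion at 30, 60" minutes and later times.
- **SAP window.** SAP 5.2 gives "Following completion of dosing + 5 to 7 minutes" for the 1 h sample. All its other post-dose PK windows count from scheduled time. SAP 8 does not list this as a change from the protocol.
- **Floor.** Note h of Table 1, which appears in both documents, reads "No sooner than 5 minutes after associated PD ECG timepoint". For the 60-minute ECG this means not before 65 minutes.
- **Reason for the delay.** Protocol 6 sets the order of procedures: "ECG extraction window (from nominal time to 5 minutes after nominal time), PK sample" and then the other assessments.
- **Expected peak.** Protocol 3.5: "The maximum concentration is anticipated to be at the end of the infusion. The concentration will decrease sharply".
- **Endpoint.** "PK parameters of MCI-186" are secondary (Protocol 2.1.4). SAP Appendix 1 takes Cmax as the maximum drug concentration and tmax as its time. Appendix 2 repeats the Cmax wording among the compartmental parameters and does not say whether it is observed or predicted.
- **Tables.** Protocol 10.4.1: "The PK concentrations will be summarized by planned sampling time". SAP 7.8.1: "Nominal sampling times will be displayed in the summary".
- **Validity.** SAP 5.3 admits only valid PK data to tables and figures and leaves their handling to data review. SAP 4 calculates parameters from adopted data only.

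**The concern.** There are two worries.

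First, one sample has two windows. If the infusion ends early, the SAP window opens before the note h floor and inside the protected ECG window. If it ends late, a sample that meets the protocol can come before the SAP window opens. It could then be judged invalid, and it is the first sample after the expected peak.

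Second, the schedule steps around the peak. The last sample before the end of infusion closes at 37 minutes and the next opens at 65, so the expected maximum is never drawn. Cmax would read low and tmax could not fall at 60 minutes. The row labelled 1 h would hold values from 65 to 67 minutes.

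The PK profile, a secondary objective, is directly at stake. Because Protocol 10.4.5 applies the 10 msec rule at the geometric mean Cmax, one would also ask whether the primary conclusion is touched.

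**Working it through.** **1. Does the schedule contain an extra end-of-infusion sample?** Protocol Table 3 gives 39 PK samples per subject. The listed times are 1 pre-dose, 5 (30, 60, 75, 90, 105 min) and 7 (2, 3, 4, 6, 8, 12, 24 h), so 13 × 3 periods = 39. The figure is reproduced and there is no extra sample. The gap runs from 30 + 7 = 37 min to 60 + 5 = 65 min.

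**2. How far apart are the windows?** Let the infusion end at 60 + d minutes. The protocol window is 65 to 67. The SAP window is 65 + d to 67 + d. The share of the protocol window inside the SAP window is (2 − |d|)/2.

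| End of infusion (min) | SAP window (min) | Share in common |
|---|---|---|
| 60 | 65–67 | 1.00 |
| 59 or 61 | 64–66 or 66–68 | 0.50 |
| 58 or 62 | 63–65 or 67–69 | 0 (they only touch) |
| ≤57 or ≥63 | ≤62–64 or ≥68–70 | none |

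So the conflict takes effect only when the actual duration differs from 60 minutes.

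**3. How low does the sampled Cmax read?** Inputs from Protocol 3.4.1: single-dose Cmax 1047.3 ng/mL and AUC 1364.7 ng·hr/mL. The documents give no rate constants, so the shape of the curve is an assumption.

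*One compartment.* 1 − exp(−k) = 1047.3/1364.7 = 0.7674, so k = 1.4585 per hour (half-life 28.5 min). The fraction of the peak left after m minutes is exp(−k·m/60):

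- 5 min: 0.886, or 927 ng/mL (11.4% low)
- 6 min: 0.864, or 905 ng/mL (13.6% low)
- 7 min: 0.844, or 883 ng/mL (15.6% low)

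*Two phases*, with weights solved to match the same Cmax and AUC, fast half-life 1 to 28 min and slow half-life 0.6 to 3 h: the highest sample is 0.804 to 0.972 of the peak, so 3% to 20% low. When the fast phase is very short, the 35–37 min sample is the highest.

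These curves do not settle where tmax falls. At mid-window the 36-minute sample is the maximum in 110 of 126 profiles with fast half-lives of 1–18 min, in 1 of 70 with 19–28 min, and in 111 of 196 overall. The count depends on the grid chosen.

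**4. What if the 1 h sample were rejected?** In the one-compartment case the next highest is the 36-minute sample, at 0.760 of the peak. 0.760/0.864 = 0.879, so that subject's Cmax falls a further 12%. Over the two-phase profiles the further fall is 0% to 12%.

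**5. Does this reach the 10 msec rule?** Protocol 3.4 expects 1041 ng/mL at 60 mg and 6117 ng/mL at 300 mg. Protocol 3.4.2 assumes that severe hepatic impairment raises exposure by at most two-fold: 2 × 1041 = 2082 ng/mL. If the two-phase fractions are carried over to 300 mg, the sampled Cmax is 0.804 × 6117 = 4918 to 0.972 × 6117 = 5946 ng/mL. Divided by 2082, that is 2.4 to 2.9 times the scenario.

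**The case for a change.** The best case for a change is that the conflict lies in the text itself and needs no modelling. Protocol 7.1.1 has start and completion times recorded, so a duration other than 60 minutes would be visible, and SAP 5.3 makes the 5.2 windows the reference for PK data. No subject excluded (SAP 4) does not mean that no single sample was rejected. Appendix 2 leaves Cmax open to two readings, and a term used in the decision rule should have one. Correcting the words would cost very little.

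Much of this is true, but it does not show that a result would differ.

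- **Duration.** Protocol 7.1.2 says the dose duration may not be changed and that departures must be recorded. No departure is shown.
- **Rejection is not automatic.** SAP 5.3 refers data handling to review, and SAP 13 says that version 2.0 reflects that meeting. Both appendices use actual sampling times, so a sample a minute off either window can enter the calculation at its true time. Protocol 6 also places time windows in a separate document, not supplied here, which may already settle the anchor.
- **Cmax in Appendix 1 is not ambiguous.** A non-compartmental maximum can only be a sampled value, and SAP 7.8.1 says predicted where it means predicted.
- **The delay is disclosed and has a purpose.** It appears in Protocol 3.5, 5.1.2, 6.4 and 6.5, in note h and in SAP 5.2, and SAP 12.1 lists the collection times. A sample at 60 minutes would disturb the ECG extraction window on which the primary endpoint depends.

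Two points stand: the anchor in SAP 5.2 differs from the protocol without being declared, and Appendix 2 does not say whether its Cmax is observed or predicted. Which Cmax enters the 10 msec rule belongs to the separate ECG SAP named in SAP 1, which was not supplied. Observed is the natural reading.

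**Conclusion.** No change to the plan follows. The window difference is a clerical slip. It has no effect at a 60-minute infusion. It can matter only if an infusion ends off time and the sample is then rejected at review, in which case that subject's Cmax would fall by up to about 12% under the assumed curves. Neither event is shown.

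Sampling 5 to 7 minutes after the expected peak is a fair trade-off that protects the ECG. The cost is a sampled Cmax about 11% to 16% below the end-of-infusion value under one compartment, or 3% to 20% under assumed two-phase curves. These sizes rest on the protocol's simulated Cmax and AUC, on a peak at 60 minutes, and on assumed curve shapes, whereas the SAP itself fits three compartments. Applying them at 300 mg further assumes a similar shape at that dose.

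Sampling, model and decision rule would stay the same under any rewording, and the 300 mg exposure remains well above the two-fold scenario. If the documents are edited for other reasons, the anchor and the Appendix 2 label can be tidied then.
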